1.1.1.1 Study Endpoint Visit (Week 8, or Endpoint)

At the conclusion of the endpoint visit, the subject will be asked to mail the Niraxx G1 Headband device back to the primary investigator. If requested, the subject will be provided with shipping materials.

Following assessments will be performed at the Week 8/Endpoint Visit:

- Urine Pregnancy Test (for females of childbearing potential)
- CGIs
- GAF
- CTAE
- Concomitant Medications
- MGH-SECS-C
- ADHD-SC
- SRS-2
- BRIEF-P
- TSRQ
- MGH-SECS-I
- CBCL

1.1.1. Post-Study Follow Up Visit (Follow Up, Week 10)

After Treatment completion, subjects will continue with one more clinical study visit after 2 weeks, to measure the long-term effect of tPBM. Post tPBM administration, subjects will be permitted to start or change treatment with existing or new medications, as clinically necessary (and at any time in the study if severe worsening of symptoms occurred – see 5.7. Study Discontinuation). Follow Up assessments will be carried out, including Clinician- and Patient-Rated assessments.

Following assessments will be performed at the Week 10 Visit:

- CGIs
- GAF
- CTAE
- Concomitant Medications
- SRS-2
- ADHD-SC
- TSRQ

1.2. Study Discontinuation

We will encourage subjects to continue enrollment in the study via follow-up visits regardless of the nature of discontinuation of the tPBM. At the end of the study, we will refer the subjects to their counselor and/or psychiatrist and will communicate clinical data upon signed authorization. If the CGI-S increases more than 2 points during the study, the subject will be counseled to start

or change to an FDA-approved medication treatment. If the CGI-S increases more than 5 points or if a subject becomes actively suicidal as per clinician judgment, termination from the study will be mandated. Subjects who are deemed actively suicidal and are in imminent danger will be escorted to Acute Psychiatric Service (the local psychiatric Emergency Department at Massachusetts General Hospital) for evaluation and subsequent hospitalization. If the subject is appropriate for outpatient monitoring, the subject will be followed with frequent appointments outside the study. Each subject will have the Investigator's contact information as well as instructions on how to call for emergency services, if needed.

If study participation is discontinued due to safety reasons, participants will receive three follow-up visits, while appropriate psychiatric follow up access is assured with their treating psychiatrist. If emergent suicidality were to occur during the course of the study, the supervising clinician will then directly assess the level of risk and take the appropriate action (including contacting treatment providers, working on a safety plan, arranging for emergency evaluation via an ER, calling 9-1-1, etc.). The clinician will document the actions taken, and it will be noted in the participant's file. Subjects who discontinue due to non-compliance with the protocol will receive a referral to treaters in the area.

A participant may withdraw consent at any time for any reason (e.g., lack of efficacy, adverse events, etc.). A subject may be withdrawn from the study by study staff at any time if any of the following conditions are met:

- Worsening of ATs, ADHD or current/emergent major psychiatric disorder.
- Subjects who experience intolerable adverse effects as determined by the PI.
- Emergent suicidality
- Pregnancy
- Failure to keep study appointments for more than 2 consecutive visits
- Failure to utilize the telemedicine platform
- Clinical judgment of the investigator

Subjects may receive three clinical follow-up visits at the completion of the study (or if they are required to discontinue for safety reasons), allowing adequate time for appropriate psychiatric referrals to treaters in their communities. Follow-up visits are optional and are at no cost to participants. These visits are not part of the clinical trial and no research data will be collected during follow-up. Subjects who fail to keep study appointments or are non-compliant may be dropped from the study. These study subjects will be given a referral to treaters in their area but will not be offered three follow-up visits.

If a subject would like us to forward their clinical history to his/her primary care physician, or a new clinician, we will forward any pertinent information with the proper completed release of information authorization form. If a subject who has come from the clinic of the investigator happens to drop out of the study, he or she will return to his or her treating physician.

Study Assessment Scales and Forms

Subjects will be evaluated at scheduled intervals. At each visit, measures of safety and efficacy will be obtained using assessments of psychiatric symptoms and functioning (CGIs, GAF) and measures of adverse effects (CTAE). At the Midpoint (end of week 4) and Endpoint study visits (Week 8 or Endpoint), additional clinician-, subject-, and informant-rated assessments will be repeated (see below for details).

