Aforementioned proof-of-concept study was blessed with a fast pace of recruitment, with 10 participants over a period of 18 months, despite its demanding nature for our patients. Even faster and more efficient recruitment along with a less demanding schedule for our patients is

Photobiomodulation for ASD in ADHD

possible. Telemedicine substitutes for face-to-face office visits through a remote, two-way video-conference through secure Internet access. Telemedicine use in the clinical setting has successfully provided specialist advice with favorable patient outcomes, satisfaction, and costs (38-41). Clinical trials are the gold standard for evaluating new therapeutic opportunities in medicine, efforts aimed at improving their efficiency are needed to facilitate patient participation in a manner that reduces dropout, and Telemedicine may offer such opportunity.

We propose an open label trial to assess the safety and efficacy of tPBM in improving ATs in ADHD youth with comorbid ATs. Eligible participants will be youth with adequately treated ADHD who present with comorbid ATs of at least moderate severity. Participants will receive tPBM daily for 8 weeks. Participants who meet eligibility criteria will be mailed the tPBM device. They will be able to administer the treatment in the comfort of home, at scheduled intervals. Accurate application of tPBM, its safety, and efficacy will be assessed during regular scheduled meetings with study clinician. These meetings will all be conducted via telemedicine with HIPAA compliant communication technology. Safety of and treatment response to tPBM will be monitored by parent- and clinician-rated measures during regularly scheduled visits. Our study will address the question whether tPBM is effective for the treatment of ATs in youth with ADHD, and whether it is acceptable among our patients.

Certain aspects of tPBM render it a feasible intervention. It can be delivered at home. It does not require ingestion of any substances. It is possible that the exposure to tPBM might be more acceptable than use of medications among some minority groups. This intervention does not require providers with specific cultural expertise or second language proficiency.

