The tPBM treatment can be completed in the comfort of participants' homes, while monitoring their safety and response during scheduled medicine visits. The advantage of the tPBM treatment approach compared to pharmacotherapy is that adherence can be easily monitored. Our study will answer whether tPBM has an effect on ASD symptoms in ADHD and whether it is acceptable among our patients, for whom frequent visits otherwise would be prohibitive or render it inaccessible. As such, we propose the inclusion of a telemedicine visits in this study protocol.

II. SPECIFIC AIMS

The purpose of this 10-week open-label clinical study is to assess the tolerability, safety, and efficacy of Transcranial LED Therapy in youth patients with ADHD diagnosis who also present with at least moderate level of ATs.

Primary Objective:

- To assess the *efficacy* of tPBM for the treatment of ATs in youth with ADHD.
- To assess the *safety and tolerability* of tPBM for treatment of ATs in youth with ADHD

Secondary Objective:

- To evaluate the efficacy of tPBM in treatment of ADHD with ATs

Rationale for use of this device in patients with ASD:

Different devices have been used in study of near-infrared radiation (NIR) treatment effects in humans. We decided to use a new device, manufactured by Niraxx for its ease of application,

Photobiomodulation for ASD in ADHD

with safeguards to pose no risk of exposure to LED light. The device is designed as a simple headband, a common garment during most sports or leisure activities

III. SUBJECT SELECTION

Inclusion Criteria

- Male or female participants between 9 and 17 years of age (inclusive)
- Participant fulfills DSM-5 diagnostic criteria for ADHD as established by the clinical diagnostic interview.
- Participants with at least moderate severity of ASD symptoms as demonstrated by SRS raw score ≥ 75 or CGI-AT severity score ≥ 4
- Participants must understand the nature of the study. Participants must sign an IRB-approved informed consent form before initiation of any study procedures.
- Participants are willing and able to cooperate with all tests, examinations and demonstrate ability to appropriately administer the study treatment required by the protocol.
- Participants must have access to a computer with camera and broadband internet connection
- Participants have access to Apple IOS in their household.

Exclusion Criteria

Subjects will be excluded from the study for **any** of the following reasons:

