Subject, parent/guardian and research staff will enter survey responses into the electronic assessment forms on REDCap. A member of study staff will send the forms for the parent/guardian to fill out via REDCap. The responses will be then transmitted securely via an encrypted connection and stored in a secured database. Electronic data capture eliminates the need for subsequent data entry by staff, thus minimizing human error. However, in the event that REDCap is unavailable or malfunctioning, study staff will print all study instruments and mail them to subjects and parent/guardian, thus study data will be collected in paper form.

Subjects will be instructed to administer daily tPBM treatments for 8 weeks. Each subject will be mailed a device to keep at home during study participation and return to study staff upon completion.

Concomitant Medications/Treatments

As part of the initial psychiatric evaluation, a detailed history of past and present treatments (pharmacological and non-pharmacological) will be obtained. At each study visit, subjects will be assessed for the use of concomitant medication. The guidelines for use of concomitant medications/treatments during the study are as follows:

- Participants may continue treatment with concomitant psychotropic medications (provided no exclusion criteria are met) and must remain on a stable dose during the course of the trial.
- Subjects requiring initiation of acute or chronic medication treatment may be discontinued from the study if treatment is judged by the investigator to interfere with the assessment of study drug effect.

- Non-pharmacological treatments such as supportive individual, family, or group therapy will be permitted provided they were in place for a substantial period of time (>1 month) prior to study enrollment and remain unchanged during the course of the trial.
- No new non-pharmacological treatments may be initiated during the course of the trial.

Washout Period

After the screening period, subjects who are currently taking any light-activated drugs, as noted in exclusion criteria, and willing to discontinue the use of their medication may do so in order to be eligible for participation in this study, if clinically appropriate per clinician judgment.

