1.2.1. Clinician-Rated Assessments

1.2.1.1. Clinician-Rated Behavioral Measures

(Administered at all visits)

- Clinical Global Impression Scale (CGI; (43)): The CGI is a measure of illness severity, improvement, and efficacy of treatment. The score for severity ranges from 1 (normal, not at all ill) to 7 (among the most extremely ill subjects). Improvement ranges from 1 (very much improved) to 7 (very much worse). The effectiveness index measures to what extent the subject is experiencing therapeutic effects in conjunction with the level of adverse events they are experiencing. CGI scales will be used for the assessment of ADHD and ATs
- Global Assessment of Functioning Scale (GAF; (44)): composite rating of an individual's overall level of functioning (1= worst to 100 = best).

(Administered at baseline and/or screening, midpoint, and endpoint)

- MGH Social-Emotional Competence Scale [Clinician-Rated Measure] (MGH-SECS-C): This is a 37-item scale that assesses change in the frequency and severity of core and associated symptoms of ASD.
- ADHD Symptom Checklist (ADHD-SC) assesses each of the individual symptoms of ADHD based on the DSM (0-3 on a scale of severity)

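### The mandatory CGI-S stop can be met only by a change from 1 to 7 on a seven-point scale, so it is effectively inert; the CGI-S rules also leave the domain and reference visit unstated

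*Combined protocol and SAP*

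**What the plan says.** Section 1.2 Study Discontinuation has two rules based on a rise in CGI-S. A rise of more than 2 points during the study leads to counselling about starting or changing medication. The stronger rule makes leaving the study compulsory: "If the CGI-S increases more than 5 points or if a subject becomes actively suicidal as per clinician judgment, termination from the study". Neither rule says which CGI-S rating it uses or which visit the rise is counted from.

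The scale is described in section 1.2.1.1 Clinician-Rated Behavioral Measures: "The score for severity ranges from 1 (normal, not at all ill) to 7 (among the most extremely ill subjects". For the companion improvement item, "Improvement ranges from 1 (very much improved) to 7 (very much worse". The same section adds that "CGI scales will be used for the assessment of ADHD and ATs", so each participant has two severity ratings. Table I schedules the CGIs at Screening and at Baseline, then at Weeks 1, 2, 3, 4, 6, 8 and 10.

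The Inclusion Criteria admit participants on "SRS raw score ≥ 75 or CGI-AT severity score ≥ 4". The background section describes the population in these words: "Eligible participants will be youth with adequately treated ADHD who present with comorbid ATs of at least moderate severity".

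Safety Monitoring has a separate rule on a different scale. A CGI-I of 6 or higher, judged against baseline, leads to the offer of an antidepressant.

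**The concern.** A rule that mandates an action should be capable of being met by the people it covers. Here the threshold takes up nearly the whole width of the scale, and the trial recruits young people whose ATs are already at least moderate. They have little or no room to rise.

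Participants are aged 9 to 17, treat themselves at home and are seen only by video. Someone reading section 1.2 would take it that a score-based backstop forces a stop if ATs or ADHD worsen badly. If that backstop cannot realistically operate, whether such a participant is stopped rests on individual judgment. Because the domain is not named, two clinicians could also apply the same rule to different ratings. Because the reference visit is not named, they could count from different starting points.

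**Working it through.** **Inputs.** Scale 1 to 7 (section 1.2.1.1). Thresholds of more than 5 and more than 2 points (section 1.2). Entry on CGI-AT severity of at least 4, or on SRS raw score of at least 75 (Inclusion Criteria). The plan gives no figure of its own to reproduce. Whole-number scoring is assumed, since the documents mention no half points.

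**Step 1: the threshold.** The largest possible rise is 7 − 1 = 6. On whole numbers, more than 5 means at least 6. Only 1 to 7 qualifies.

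**Step 2: room to rise.** From starting score b, the largest rise is 7 − b.

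| Starting score | Largest rise | More than 2 reachable? | More than 5 reachable? |
|---|---|---|---|
| 1 | 6 | yes | yes |
| 2 | 5 | yes | no |
| 3 | 4 | yes | no |
| 4 | 3 | yes, at 7 only | no |
| 5 | 2 | no | no |
| 6 | 1 | no | no |
| 7 | 0 | no | no |

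**Step 3: apply the entry criteria.** Counted from baseline on the AT rating, a participant entering with CGI-AT of 4 or more can rise by at most 3 points, so the mandatory stop is out of reach. A participant admitted on the SRS score alone could have a lower CGI-AT, but would need to start at exactly 1. The ADHD rating has the same requirement. Adequately treated ADHD may give low starting scores there, but the documents give no CGI distribution.

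**Step 4: the unstated reference.** If the rise were counted from the lowest score in the study, a participant entering at 4 would first have to improve by 4 − 1 = 3 points, to 1, and then reach 7. The limb becomes conceivable but remains remote.

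**Step 5: the counselling rule.** Read from baseline, the more-than-2-points rule cannot act from 5, 6 or 7, and from 4 it needs the scale maximum.

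**Step 6: other provisions for worsening.**
- Section 1.2 lists worsening of ATs or ADHD as a ground on which staff may withdraw a participant. This is discretionary and has no score.
- Safety Monitoring: CGI-I of 6 or more leads to a medication offer, not a stop.
- Reporting Procedures for All Adverse Events, and Monitoring and Quality Assurance: withdrawal or dose reduction for adverse events, on judgment.
- Section 1.2 and the paragraph on depression, suicidality and manic switch: mandatory stops for active suicidality and for mania or hypomania. These are clinical events, not AT or ADHD scores.

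None of these is a mandatory score-based stop for AT or ADHD worsening.

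**The case against.** The strongest reply is that the practical gap is small. Staff may withdraw anyone whose ATs or ADHD worsen, with no score required, which is a lower bar than any threshold. The CGI-I rule is attainable from every entry severity. The suicidality and mania stops are mandatory, and the investigator reviews adverse events weekly. Nothing in the documents requires a score-based stop, and CGI-I is itself a clinician's judgment. All of this stands and limits the point. It does not rescue the limb: the protocol chose to state a mandatory threshold, and that threshold does not work. A CGI-I criterion leaves judgment in the rating but removes discretion over the action.

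A second objection also stands. The limb ends study participation, whereas the opening of section 1.2 asks that participants be encouraged to stay in follow-up however tPBM came to be stopped. A replacement that simply produced more study terminations would cut against that and lose later SRS-2 ratings.

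Four stronger readings are tempting but unsupported.
- A reader might infer that the limb is strictly impossible. It is not: the SRS entry route, the ADHD rating and the open reference visit leave a change from 1 to 7 conceivable.
- A reader might infer that participants have no protection against worsening. The provisions listed in the working show otherwise.
- The Post-Study Follow Up section points to Study Discontinuation with the words "at any time in the study if severe worsening of symptoms occurred". A reader might take this as promising a mandatory stop, but the sentence concerns when medication may be started or changed.
- A reader might infer that the primary result is compromised. The limb as written does not affect the primary analysis of SRS-2 total raw score.

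**Conclusion.** The point holds in a limited form. The only mandatory score-based stop for AT or ADHD worsening requires a change from 1 to 7. Counted from baseline on the AT rating, no participant entering with CGI-AT of 4 or more can meet it. The two CGI-S rules also lack a stated domain and reference visit, and read from baseline the counselling rule has no effect from scores 5 to 7.

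The defect lies in this one safeguard, not in safety monitoring as a whole. The arithmetic assumes whole-number scoring; the 3-point ceiling from an entry score of 4 does not depend on that assumption. No share of participants can be stated, because the documents give no distribution of CGI scores. Severity is minor to should-fix.

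**What to change.** Amend section 1.2 Study Discontinuation as follows.

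1. Replace the more-than-5-points limb with an attainable criterion on a rating already made at every visit and already tied to baseline. One example is CGI-I of 7 at any visit, on either the AT or the ADHD rating, with the study clinicians confirming the threshold. A single CGI-I of 6 keeps its present action under Safety Monitoring.
2. Make the mandated action discontinuation of tPBM, with scheduled follow-up continued where the participant agrees. The Week 8 and Week 10 SRS-2 can then still be collected. Anyone who does leave the study is already covered by the exit visit under Withdrawal from the Study.
3. Keep the active-suicidality limb unchanged.
4. State the domain and the baseline reference for the new rule and for the more-than-2-points rule. The counselling threshold itself need not change. Prompting more medication changes would conflict with the requirement that participants on psychotropic medication "must remain on a stable dose during the course of the trial".

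The cost is a wording amendment with no new assessments. The downside is that some participants, in a number the documents do not allow to be estimated, may stop the device early because of worsening related to the outcome. Their exposure would be shorter, and these stops should be reported.
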